8.3. Change from baseline

Change from baseline in a measurement is calculated as:

Change = measurement at post-baseline visit – measurement at baseline.

Annualized rate of change (Slope) = 365.25 *((measurement at post-baseline visit –

measurement at baseline)/(date of post-baseline visit – date of baseline visit + 1)).

8.4. Visit windows

The visit windows around the bi-weekly visits will range from +/- 3 days through Week 10,

and +/- 7 days through Week 52. Data will be summarized based on the eCRF (Study Visit) in

which it was collected. Data collected as an unscheduled visit will be re-assigned to a Study

Visit based on the SAP visit windows specified. If a subject has multiple values of the same

efficacy data within a visit, the worst case data will be used. If a subject has multiple values

of the same safety data within a visit, the average of the multiple records will be used. Data

from all assessments will be listed.

8.5. Sample size determination and power calculation

The sample size for this study is approximately 51 subjects in Parts A and B combined. The

rationale for the sample was based on both clinical and statistical considerations. Based on

the comparison of the NIH phase 1 subjects and similar subjects in the NIH natural history dataset, approximately 51 subjects: 16 on sham and 35 on active treatment will allow for the detection of a clinically relevant difference of the sum of the 4 NPC-SS domains that make up the composite outcome.

The power calculation was based on the primary endpoint, defined as the change from baseline at week 52 in the VTS-270 group compared to the sham group in the composite outcome that is the sum of the ambulation, cognition, fine motor, and swallowing scores of the NPC-SS. This outcome ranges between 0 and 20 at each assessment. Positive values for this change indicate a decline in function whereas negative values indicate improvement. The assumptions for the calculation of the power are as follows:

- The VTS-270 group has an average increase in value over 52 weeks ranging from 0 points to 0.2 points. Taking the greatest decline of this range, the estimate of (composite outcome at week 52) (composite outcome at baseline) = 0.2
- The sham group has an average increase in value over 52 weeks ranging from 1.6 points to 1.9 points. Taking the least decline of this range, the estimate of (composite outcome at week 52) (composite outcome at baseline) = 1.6.
- A common standard deviation of 1.64.
- The sample size in the VTS-270 group is 35 and the sample size in the sham group is 16.
- Two-sided alpha = 0.05.

Based on these assumptions, an analysis of covariance (ANCOVA) will have 79% power to detect a statistically significant difference between the VTS-270 and sham groups.

Three additional subjects above the planned sample size were enrolled into the study, such that there were 54 subjects randomized. Assuming a 5-10% drop out rate, the number of completers could range from 48-51. Thus, the power of the trial, based on the parameters above, could range from 76% if 48 subjects complete to 79% if 51 subjects complete.

Six different scenarios are presented in Table 1. These are various differences based on an assumed average increase of 0 to 0.2 points in the composite outcome in the VTS-270 group

August 27, 2018 Page 26

over a 12-month period and an average increase in the composite outcome ranging from 1.6 to 1.9 points in the sham group. Thus, the difference in the change from baseline to 52 weeks for the two groups ranges from 1.4 to 1.9 (this is based on 1.6 - 0.2 and 1.9 - 0). In general, the study is well-powered to detect differences that are similar to those that were observed between the Phase 1/2a and natural history study with the power for the scenarios presented below ranging from 0.79 to 0.96.

Table 1. Estimated power for the VTS301 protocol where VTS-270 group is assumed to increase 0 to 0.2 points over 1 year

Estimated difference in change from baseline for the VTS-270 group compared to sham

1.9 points

1.8 points

1.7 points

1.6 points

1.6 points

1.5 points

1.5 points

1.5 points

1.6 points

1.7 points

1.8 points

1.9 points

1.8 points

1.8 points

1.9 points

1.8 points

1.9 points

1.8 points

1.9 points

0.79

No formal power calculation was performed for clinician CGIC.

8.6.Pooling of investigator sites

1.4 points

Analyses will not be stratified by site since the study has many investigative sites (20) relative to the anticipated number of randomized subjects (51) as NPC is an ultra-rare orphan disorder. All sites use the same protocol, entry criteria, data collection methods, and endpoints and are monitored to verify compliance with the protocol. The NPC-SS will be assessed and scored centrally for all subjects across sites, and this blinded centralized scoring will be used for all NPC-SS efficacy analyses. According to Meinert (1986), these criteria justify pooling results across centers [4].

8.7.Stratification

Although randomization in Part B is stratified by miglustat use and baseline NPC-SS level to ensure balance across the 2 treatment groups, the statistical analyses will not be stratified

based on these variables. The number of subjects in any one stratum may be too small to

make any meaningful comparative inferences.

All formal statistical analyses will be stratified by whether the subject entered the study in Part

A or entered in Part B.

In order to understand the effects of stratification, the following stratification groups will be

used as sensitivity analyses:

Subjects randomized in Part A

• Subjects randomized in Part B, miglustat use +, NPC-SS total score ≥ 20

• Subjects randomized in Part B, miglustat use -, NPC-SS total score ≥ 20

Subjects randomized in Part B, miglustat use +, NPC-SS total score < 20

• Subjects randomized in Part B, miglustat use -, NPC-SS total score < 20

8.8.Safety parameters

All safety summaries will present data by study part. Summaries will present adverse

events, including those related to the study treatment and administration procedure. Serious

adverse events will be summarized similarly and include narratives as well. Clinical

laboratory, vital sign and ECG values and changes from baseline will be summarized by

treatment group and time point. Physical examination abnormal results will be listed and

summarized. Results of several audiologic evaluations and ABR will be summarized and

presented.

In addition to the above assessments, the following safety evaluations will be conducted for

the device safety and tolerability substudy in Part C:

Wound check, examination of port site and catheter track at access port infusion visits

• Intracranial pressure (ICP) via LP

9. Study population summaries

9.1.Enrollment

Enrollment will be summarized by treatment group. A table will present the number and

percentages of subjects in each stratum by treatment group. A listing of screen fail subjects

with reason for screen fail will be provided.

9.2.Subject disposition

The disposition of subjects (number randomized but did not receive study drug, number

randomized and received all study drug procedures, number randomized but who did not

receive all study drug procedures) will be tabulated by study part and treatment group and

presented in a CONSORT diagram. All possible reasons for not receiving all study drug

procedures will be summarized by study part and treatment group.

Listings will present time to and reason for discontinuation or withdrawal by study part,

treatment group and subject.

The analysis population table will summarize the number and percent of subjects in the

following populations:

ITT

mITT (primary population for efficacy assessments)

Per Protocol

Safety Population.

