Page 30

concomitant unless it can be determined that the medication end date occurred prior to the first dose of study medication. If the medication start date is partially missing and the partial date is not sufficient to determine if the medication was taken after the first dose of study medication, then the medication will be considered concomitant for the study unless it can be ruled out by the partial date and/or medication end date.

The number and percent of safety subjects using concomitant medications will be tabulated by drug class, study part and treatment group. All prior and concomitant medications will be listed.

10.2.Duration of treatment and exposure to study drug

Duration of treatment will be defined as the length of time from first dose of study administration to date of discontinuation from the study treatment within each study part (Part A/B combined and Part C). That is, (Date of last dose during study part treatment period – Date of first dose of study drug during study part + 1 day). Exposure to VTS-270 will be calculated as the total dose (mg) received during the study part (Part A/B combined or Part C). Standard descriptive statistics will be used to summarize duration and exposure by study part and treatment group using the safety analysis set.

Compliance to study medication will be calculated as 100 × (number of times a subject received study medication)/(Expected number of times a subject was to receive study medication per the protocol schedule while participating in the trial). Compliance will be calculated separately for each study part (A/B combined and C). All dosing information will be listed by study part, treatment group and subject ID. Study drug administration over time will be summarized in a listing showing VTS-270 dose at each scheduled clinic visit and/or IT administration.

11. Efficacy analyses

The statistical methods described below apply to the analyses performed for Part B. All Part C data will only be listed and summarized.

VTS301: STATISTICAL ANALYSIS PLAN August 27, 2018 Page 31

11.1.Co-primary efficacy analyses

The co-primary efficacy endpoints are as follows:

- Change from baseline in NPC-SS composite score at Week 52 in the group treated with VTS-270 vs. the sham control group
- The Blinded Clinician CGIC at Week 52 in the group treated with VTS-270 vs. the sham control group

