The NPC-SS composite score is the sum of the ambulation, cognition, fine motor, and swallowing domains of the NPC-SS. This outcome ranges in value from 0 to 20 points at each assessment. Measurements at baseline, each post-baseline measurement through Week 52, and change from baseline for each measurement through Week 52 will be summarized descriptively. For the co-primary efficacy analysis, any missing Week 52 assessments will be imputed. Subjects who take the rescue option will be considered dropouts and will need to have their missing Week 52 assessment imputed. To protect against the potential bias that may occur if outcomes for the completers are different from those for the non-completers (i.e., missing not at random; MNAR), the approach taken will be to impute all missing observations from either treatment arm as if they came from the sham group. That is, the average change from baseline for the sham group will be added to the baseline observation of each subject with a missing assessment at Week 52. The missing value imputation will occur at the individual domain level. An ANCOVA, with treatment group, study part, and baseline NPC-SS composite score included in the model, will be performed to test for differences in the change from baseline to Week 52 between VTS-270 and sham groups in the co-primary efficacy outcome measure. Considering the small sample size, this ANCOVA will be performed using a nonparametric approach such that the outcome data will be ranked. Average ranks will be assigned in case of ties. The null hypothesis will be $H_0: \Delta_d - \Delta_s = 0$, and the alternative hypothesis will be H₁: Δ_d - $\Delta_s \neq 0$, where Δ_d is the mean rank of the change from baseline for the drug VTS-270 group and Δ_s is the mean rank of the change from baseline for the sham group. The null hypothesis will be tested with both means adjusted for study part in which the subject was randomized to (A or B) and baseline NPC-SS composite score. This test will be performed at α =0.05 level (two-sided) of significance.

August 27, 2018

Page 32

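### SAP 8.5 presents power for the NPC-SS composite alone as the power of the trial, although both co-primary nulls must be rejected to reach the key secondaries

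*SAP*

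**What the plan says.** SAP 8.5 names a single endpoint as the basis of the calculation: "The power calculation was based on the primary endpoint, defined as the change from baseline at week 52 in the VTS-270 group", compared with sham, in the four-domain NPC-SS composite. Its inputs are mean changes of 0.2 points (VTS-270) and 1.6 points (sham), "A common standard deviation of 1.64", 35 and 16 subjects, and two-sided alpha 0.05. The stated result is 79%.

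The section then allows for 54 randomized subjects and 5-10% dropout, and concludes: "Thus, the power of the trial, based on the parameters above, could range from 76% if 48 subjects complete", with 79% for 51 completers. Table 1 runs from 0.79 at a 1.4-point difference to 0.96 at 1.9 points under the title "Estimated power for the VTS301 protocol where VTS-270 group is assumed to increase 0 to 0.2 points over 1 year". The text introducing it says: "In general, the study is well-powered to detect differences that are similar to those that were observed" between the Phase 1/2a and natural history studies. The section closes its power discussion with "No formal power calculation was performed for clinician CGIC".

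SAP 11.1 opens with "The co-primary efficacy endpoints are as follows" and lists two: the composite change and the blinded Clinician CGIC, both at Week 52. The protocol synopsis lists the same pair. The composite is tested at two-sided 0.05 and no division of alpha is described. SAP 11.3 allows the key secondary tests only if both co-primary nulls are rejected, and treats the first of them as exploratory if either co-primary misses two-sided 0.05.

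**The concern.** A figure described as the power of a trial is normally read as the chance that the trial meets its primary objective. Here that objective has two co-primary endpoints, and the confirmatory sequence continues only when both succeed. The figure given is the chance of succeeding on one of them. Section 8.5 refers to a primary endpoint in the singular and does not mention the Section 11.3 rule, so the reader has to combine three sections to see that 76-79% answers a narrower question than its label suggests.

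What is at stake is interpretation. If one co-primary succeeds and the other fails, or both fail, 76-79% could be quoted as the planned chance of success or of reaching the key secondaries. The supplied text gives no such figure.

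**Working it through.** **Step 1. Reproduce the stated figures from composite inputs only.** All inputs are from SAP 8.5: difference 1.6 − 0.2 = 1.4; SD 1.64; two-sided alpha 0.05. The method is two-sample t power from the noncentral t distribution, with noncentrality difference / (SD × √(1/n₁ + 1/n₂)) and n₁ + n₂ − 2 degrees of freedom.

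- 35/16: √(1/35 + 1/16) = 0.3018; noncentrality 1.4 / (1.64 × 0.3018) = 2.83; power 79.2% (stated 79%).
- 48 completers: the SAP gives no split. At 33/15, √(1/33 + 1/15) = 0.3114; noncentrality 1.4 / (1.64 × 0.3114) = 2.74; power 76.5% (stated 76%). At 32/16 it would be 77.9%.
- Charging two more degrees of freedom for the covariates gives 79.1% (35/16) and 76.5% (33/15).
- 1.9 points at 35/16: noncentrality 1.9 / (1.64 × 0.3018) = 3.84; power 96.4% (stated 0.96).
- Completers: 54 × 0.95 = 51.3 and 54 × 0.90 = 48.6, consistent with the stated 48-51.

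The figures agree to within rounding and contain no CGIC component.

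**Step 2. Bound the chance of rejecting both nulls.** Let p₁ be composite power and p₂ be CGIC power. Whatever the dependence between the tests,

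max(0, p₁ + p₂ − 1) ≤ P(both rejected) ≤ min(p₁, p₂).

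With p₁ = 0.76 to 0.79, P(both rejected) is at most 76-79% at 1.4 points. It equals p₁ only if every composite success is also a CGIC success. The bound needs no assumption about the CGIC, but it takes the SAP's composite figure as given.

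**Step 3. Illustration under assumed inputs.** The documents give neither a CGIC effect nor a correlation. Both are assumed here: p₂ from 60% to 90%, and correlation ρ between the two test statistics from 0 to 0.9. Joint power is taken as the bivariate normal probability Φ₂(z(p₁), z(p₂); ρ). At ρ = 0 this is the product, for example 0.76 × 0.60 = 0.456.

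| Composite power | Assumed CGIC power | ρ = 0 | ρ = 0.5 | ρ = 0.9 |
|---|---|---|---|---|
| 76% | 60% | 45.6% | 52.0% | 58.7% |
| 76% | 80% | 60.8% | 65.9% | 72.5% |
| 76% | 90% | 68.4% | 71.8% | 75.5% |
| 79% | 60% | 47.4% | 53.4% | 59.2% |
| 79% | 80% | 63.2% | 68.0% | 74.4% |
| 79% | 90% | 71.1% | 74.3% | 78.2% |

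The range is about 46% to 78%. It shows how much the answer depends on what the plan leaves open and does not estimate this trial's power.

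**The case against.** The best defence is that Section 8.5 already discloses what matters. It says the calculation rests on the composite, names its four domains, ties the 76-79% to the parameters listed just above, and states "No formal power calculation was performed for clinician CGIC". The well-powered remark refers to the composite differences of 1.4 to 1.9 points set out immediately before it, and the Table 1 title is qualified by the assumed change on VTS-270. A careful reader of the whole section would not be misled about which endpoint was powered. In addition, no sentence in the supplied text says outright that trial success requires both co-primaries, and all 54 subjects had been randomized when the SAP of August 27, 2018 was written, so no design decision depends on the label.

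Most of this stands and keeps the point minor. It does not remove the point. The CGIC disclosure neither withdraws the trial-level label nor mentions that the key secondaries depend on both tests. That dependence is explicit in Section 11.3, even without a general definition of trial success.

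**Conclusion.** The point holds as a mislabelled power figure, not as an arithmetic error. The 76-79% is power for the NPC-SS composite. On the SAP's own composite figures it is an upper limit, at a 1.4-point difference, on the chance of rejecting both co-primary nulls. The true joint figure is lower unless every composite success is also a CGIC success, and it cannot be computed from the supplied text. The 46-78% range rests wholly on assumed CGIC power and correlation.

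Three stronger readings are tempting but not supported:

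- *Joint power is below 80% whatever the CGIC effect.* The cap holds only at 1.4 points and only if the stated composite figure is right for the planned test; Table 1 reaches 0.96 at 1.9 points. The power section also sets no 80% target.
- *The composite figure itself is overstated, because the planned analysis ranks the data and will "impute all missing observations from either treatment arm as if they came from the sham group".* The direction is open. Giving VTS-270 dropouts the sham mean change tends to lower power. Baseline adjustment would raise it if 1.64 is the raw SD of change. The SAP does not say whether 1.64 is raw or residual, and gives neither the baseline correlation nor the dropout split by arm.
- *The trial is underpowered, or the CGIC gap is concealed.* The first cannot be shown without a CGIC effect; the second is contradicted by the disclosure in Section 8.5.

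**What to change.** Edit SAP 8.5 only.

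1. In the completers sentence, replace the trial-level subject with *the power for the NPC-SS composite co-primary endpoint alone*, and retitle Table 1 to match. Where the section speaks of a single primary endpoint, write *the NPC-SS composite co-primary endpoint*. Limit the well-powered statement to that endpoint.
2. Add one sentence: *Power to reject both co-primary null hypotheses, and so to reach the key secondary tests under Section 11.3, is no higher than the composite figure and was not evaluated.* Alternatively, report joint power over a stated range of assumed CGIC effects and correlations.

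The cost is a few lines of SAP text, plus a short calculation if the joint range is reported. Enrolment, tests and alpha do not change. The downside is a less favourable stated figure for the trial as a whole.

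### The 76–79% power in SAP 8.5 is for an unranked comparison of completers, not for the planned rank ANCOVA with sham-mean imputation; under normal change and neutral dropout the planned test has about 3–4 points less

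*SAP*

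**What the plan says.** SAP 8.5 lists its inputs:

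- "Two-sided alpha = 0.05".
- "The VTS-270 group has an average increase in value over 52 weeks ranging from 0 points to 0.2 points", of which 0.2 is used.
- "The sham group has an average increase in value over 52 weeks ranging from 1.6 points to 1.9 points", of which 1.6 is used.
- "A common standard deviation of 1.64".
- "The sample size in the VTS-270 group is 35 and the sample size in the sham group is 16".

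It attributes the resulting 79% to an ANCOVA. It then notes that 54 subjects were randomised, allows 5–10% dropout, and says that power "could range from 76% if 48 subjects complete to 79% if 51 subjects complete". The text around Table 1 gives 0.79 to 0.96 across differences of 1.4 to 1.9 points and calls the study well powered.

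SAP 11.1 defines the primary test of the same endpoint. The model contains treatment, study part and baseline composite, and "this ANCOVA will be performed using a nonparametric approach such that the outcome data will be ranked". For missing Week 52 values the rule is to "impute all missing observations from either treatment arm as if they came from the sham group", done by adding the average sham change to the subject's baseline. Subjects who take rescue are handled as dropouts. SAP 6.2 makes the mITT the primary efficacy population, so these subjects stay in. The unranked ANCOVA is a sensitivity analysis (11.2), and the completers analysis is exploratory (11.6).

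**The concern.** Section 8.5 deals with dropout by shrinking the sample and then quotes power for an unranked comparison. Section 11.1 does neither, and 8.5 mentions neither ranking nor imputation. The quoted power therefore belongs to an analysis that is not primary.

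Two features of the planned test could cost power. Ranking loses some efficiency when the data are normal. A VTS-270 subject set to the sham mean contributes no treatment effect, so losses on that arm weigh more than a smaller sample would suggest. A reader interpreting a non-significant composite result would look to 8.5 for the chance of missing a 1.4-point effect. This is separate from the question of joint power for the two co-primary endpoints; it concerns the composite test alone.

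**Working it through.** **1. Reproducing the SAP's figures.** Two-sample t-test, two-sided 0.05, noncentrality = difference / (SD × √(1/n₁ + 1/n₂)).

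- 35 and 16: √(1/35 + 1/16) = 0.3018; 1.4 / (1.64 × 0.3018) = 2.83 on 49 df. Power 79.2% (stated 79%).
- 33 and 15: √(1/33 + 1/15) = 0.3114; 1.4 / (1.64 × 0.3114) = 2.74 on 46 df. Power 76.5% (stated 76%).
- 35 and 16, difference 1.9: 1.9 / (1.64 × 0.3018) = 3.84. Power 96.4% (stated 0.96).

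A normal approximation gives 80.8% and 78.3% for the first two, a worse match. The stated figures contain no ranking, no imputation and no gain from a covariate.

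**2. Inputs for the planned analysis.** From the SAP: difference 1.4, SD 1.64, 54 randomised, 51 or 48 completers (3 or 6 missing). Assumed, because the documents do not give them:

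- a 37:17 split (Part A 9:3; the other 54 − 12 = 42 at 2:1, so 28:14), with 36:18 as a variant;
- all 54 in the mITT;
- normal change, continuous or rounded to integers;
- non-informative dropout of 2 VTS-270 + 1 sham, or 4 + 2, which is the pattern implied by 35/16 and 33/15 completers out of 37/17;
- no correlation between baseline and change.

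Each simulated trial set missing values to the observed sham mean change, ranked with average ranks for ties, and fitted treatment, part and baseline. Imputation was at composite level. This equals the SAP's domain-level rule when all four domains are missing together.

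**3. Result.** About 75–76% with 3 missing and 71–73% with 6, over both splits and both forms of change.

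**4. Where the gap arises** (37:17, continuous normal change):

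| Analysis | 3 missing | 6 missing |
|---|---|---|
| Two-sample t, completers | 79.2% | 76.5% |
| Unranked ANCOVA, completers | 77.9% | 75.6% |
| Rank ANCOVA, completers | 76.0% | 73.3% |
| Rank ANCOVA, sham-mean imputation | 75.5% | 71.9% |

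Ranking is the largest step (about 2 points). Fitting two terms that explain nothing costs about 1 point. Imputation on top of ranking costs 0.5 and 1.4 points. Without ranking, imputation gives nearly the same power as removing dropouts: about 78–78.5% and 74–76% across runs and splits.

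**5. Sensitivity of the planned analysis:**

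| Change of assumption | 3 missing | 6 missing |
|---|---|---|
| All missing on VTS-270 | 70–72% | 63–65% |
| All missing on sham, at random | about 81% | about 81–83% |
| Baseline correlation 0.3 | about 79% | about 75% |
| Baseline correlation 0.5 | about 84–85% | about 80–81% |
| t with 5 df | 84% | 80% |
| t with 10 df | 78% | 76% |
| Gamma, shape 2, right or left skew | 84–86% | 82% |
| Uniform | 69% | 64% |

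With differences of 1.6 to 1.9 and the neutral assumptions, power is about 83–95%. Simulated type I error is 4.6–5.0%.

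**The case against.** The strongest reply is that the documents give only means and an SD, so the direction of the error is not fixed. The NPC-SS domains skip levels (SAP Table A1: ambulation and fine motor go from 2 to 4, cognition from 1 to 3), so normal change is not the obvious model. With heavier tails or marked skew, ranking gains power and the planned test exceeds 79%. If 1.64 is a raw SD, a modest baseline correlation nearly restores the stated figures, and the SAP does not say whether 1.64 is raw or adjusted. Dropout could also fall mainly on sham, since rescue counts as dropout. All of this stands. A reader might infer that the true power is simply 75% or 72%; the documents do not support that as an unconditional statement.

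A reader might also infer that sham-mean imputation is the main cause. At a 2:1 dropout split it is not, as the unranked comparison shows. It becomes important when losses concentrate on VTS-270.

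Sham-side dropout is not reliably favourable either. Rescue requires worsening on all four components (SAP 4.1), hence at least 4 composite points, and imputation would replace that decline with the average of the remaining sham subjects. In one simulation with the three worst sham subjects missing, power was 56%.

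Finally, all 54 subjects were already randomised when this SAP was dated, so a restated figure cannot alter the design. That limits the consequence, but the figure still matters for reading a negative result.

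**Conclusion.** The mismatch is established from the SAP alone: 8.5 gives the power of an unranked completer comparison, and 11.1 makes a rank ANCOVA with sham-mean imputation primary. Its size is conditional. Under the SAP's inputs and the neutral assumptions in step 2 of the working, the planned test is about 3–4 points below the stated 79% and 76%. Across plausible alternatives power runs from about 63% to 86%, so 79% is not supported as a floor, nor is it shown to be too high in every case.

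The shortfall is modest and concerns the least favourable effect that the SAP considers. A reader might take this as evidence that the test is invalid or the trial inadequately sized. The simulated type I error and the power at larger differences do not support that.

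**What to change.** Restate the power sentence in 8.5, and the matching Table 1 entries, from a simulation of the analysis in 11.1: rank ANCOVA on the mITT with treatment, part and baseline, and missing values in either arm set to the sham mean change. State the assumed outcome distribution, the dropout split by arm (including how rescue is represented) and the baseline–change correlation, and say whether 1.64 is a raw or adjusted SD. Report the range across these assumptions rather than one number, and do not present 79% as the floor. If the existing figures are kept, label them as power for an unranked completer comparison.

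The cost is a short simulation and a few lines of SAP text. The stated power may look less favourable. The test, alpha and sample size stay as they are.
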